7.7. Immunogenicity Analyses

Immunogenicity variables include anti-AUX-I/anti-AUX-II binding antibody results. Binding antibody levels will be determined from samples collected on Day 1 Day 71 and Day 360.

Descriptive statistics (percent of positive measurements and average antibody level) will be presented for anti-AUX-I and anti-AUX-II antibody levels at each time point by region treated, treatment course and overall. Average antibody levels will be summarized on logarithmically transposed titer values.

In addition, a subset of these immunogenicity samples will be analyzed for neutralizing antibodies by calculating the frequency count of the positive samples and the negative samples and the percentage of samples in each category.

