14.7.1. Anti-AUX-I and Anti-AUX-II Antibodies

Serum samples will be collected and may be tested for binding and neutralizing anti-AUX-I and anti-AUX-II antibodies at visit 1 and visit 4. Additionally, if a subject consents to treatment in the open-label study, serum samples for antibody testing will be collected before injection at treatment visit 1 and at end of treatment/ early termination visit 4 of the open-label treatment period. A subset of subject samples may have neutralizing antibodies tested from Day 1 and Day 71 visits; additional samples may be analyzed if results or clinical signs warrant testing.

The serum samples obtained will be processed, stored and then shipped on dry ice to the designated central clinical laboratory before forwarding to Endo's appointed laboratory for the determination of anti-AUX-I and anti-AUX-II antibodies according to the Laboratory Manual.

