1.3.2. Secondary Objectives

The secondary objectives of this study are:

- To evaluate safety and immunogenicity of re-treating or re-dosing a subject that had previously received treatment with EN3835
- To evaluate the durability of response to EN3835 in EFP severity over the 12-month post initial dosing of EN3835 in subjects previously receiving active treatment in study EN3835-201 using the PR-PCSS and the CR-PCSS
- To evaluate the durability of response to EN3835 in EFP severity beyond 12-month post initial dosing of EN3835 in subjects previously receiving active treatment in study EN3835-201 using the PR-PCSS and the CR-PCSS
- To evaluate long-term response to EN3835 in assessments of EFP including subject satisfaction, Investigator Global Aesthetic Improvement Scale (I-GAIS), and Subject Global Aesthetic Improvement Scale (S-GAIS)
- To assess cellulite severity assessments in quadrants treated in this study with EN3835
- To evaluate immunogenicity after exposure to EN3835

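### SAP 7.7 summarizes neutralizing antibody only as a percentage of tested samples, with no visit, course, prior-exposure or per-woman denominator, so it cannot show how many women develop it

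*Combined protocol and SAP*

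**What the plan says.** SAP 7.7 has two parts. The binding-antibody part takes serum from three visits ("Binding antibody levels will be determined from samples collected on Day 1 Day 71 and Day 360") and summarizes it "at each time point by region treated, treatment course and overall". The last paragraph then adds the neutralizing assay: "a subset of these immunogenicity samples will be analyzed for neutralizing antibodies by calculating the frequency count of the positive samples" and of the negative ones, with "the percentage of samples in each category". It says nothing more about visit, course, which of the two collagenases is concerned, or how the subset is chosen.

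Protocol Amendment 2, 14.7.1, names the visits for that subset: "A subset of subject samples may have neutralizing antibodies tested from Day 1 and Day 71 visits". It goes on: "additional samples may be analyzed if results or clinical signs warrant testing". The same section places the Day 1 draw before the injection at treatment visit 1 and the other draw at the end-of-treatment visit.

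Two secondary objectives in SAP 1.3.2 concern immunogenicity. One is about re-treating or re-dosing women who have already had the drug; the other is "To evaluate immunogenicity after exposure to EN3835".

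**The concern.** EN3835 is a foreign protein given repeatedly. For neutralizing antibody, a reader of the study report will want to know two things: how many women had it before the open-label dose, and how many who lacked it then acquired it. Both are questions about women at a given visit, and the second needs both of a woman's results.

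A percentage of tested samples answers neither. It moves with the mix of samples sent to the assay: down as more Day 1 sera are tested (if Day 1 positivity is lower), up if sera picked because of a reaction or a high titer are counted. A woman with two courses can contribute several samples. Two studies with the same biology could report quite different figures, and two with different biology could report the same one.

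**Working it through.** **What the text fixes**

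1. *Unit.* SAP 3.1 makes subjects the default denominator unless a section says otherwise. SAP 7.7 does say otherwise, by naming samples. SAP 7.6, just before it, counts subjects with abnormal laboratory values.
2. *Breakdown.* The binding paragraph names time point, region and course. The neutralizing paragraph names none of them.
3. *Prior exposure.* Protocol 17.2 separates women by parent-study treatment. SAP 9 replaces those cohorts with phases and populations, and SAP 7.7 does not bring the split back for either assay.
4. *Selection.* Neither SAP 7.7 nor protocol 14.7.1 gives a subset size or a rule for choosing it.
5. *Added samples.* Protocol 14.7.1 allows testing prompted by results or clinical signs. The SAP has no rule for handling those samples.
6. *Pairing.* No within-woman comparison of Day 1 with Day 71 is planned.
7. *Shared serum.* Under SAP Table 3, footnote m, no new Day 1 antibody sample is drawn when a second course starts on Day 71 of the first. One serum is then both post-course 1 and pre-course 2, and SAP 7.7 does not say how it counts.

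**Illustration**

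The plan states no neutralizing-antibody figure, so there is none to reproduce. Every value below is an assumption. Let p0 and p1 be the proportions positive at Day 1 and Day 71, with n women sampled at both visits, and let k added samples be positive with probability q.

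- Single percentage over both visits: (n·p0 + n·p1 + k·q)/(2n + k). With k = 0 this is (p0 + p1)/2.
- Conversion among women negative at Day 1, if Day 1 positives stay positive: (p1 − p0)/(1 − p0).

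| p0 | p1 | One percentage, k = 0 | Conversion |
|---|---|---|---|
| 0% | 50% | 25% | 50% |
| 0% | 90% | 45% | 90% |
| 10% | 50% | 30% | 44.4% |
| 10% | 90% | 50% | 88.9% |
| 50% | 90% | 70% | 80% |

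The single percentage does not identify conversion. It is 50% for p0 = 10%, p1 = 90%, where conversion is 88.9%. It is also (0.5 + 0.5)/2 = 50% for p0 = p1 = 50%, where conversion is (0.5 − 0.5)/(1 − 0.5) = 0%.

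It also depends on which visits are tested. With p0 = 0% and p1 = 90%, adding a Day 360 sample per woman at the Day 71 rate moves it from 45% to (0 + 0.9 + 0.9)/3 = 60%.

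Effect of added samples, if they were counted, with n = 50, k = 20 and q = 95%:

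- Both visits, p0 = 0%, p1 = 50%: (0 + 25 + 19)/120 = 36.7%, against 25%.
- Both visits, p0 = 0%, p1 = 90%: (0 + 45 + 19)/120 = 53.3%, against 45%.
- Day 71 alone, p1 = 50%: (25 + 19)/70 = 62.9%.
- Day 71 alone, p1 = 90%: (45 + 19)/70 = 91.4%.

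So enrichment matters at moderate positivity, even within one visit, and hardly at all when nearly everyone is positive.

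**The case against.** The strongest reply is that the SAP nowhere says visits are combined. The neutralizing paragraph follows directly on one that reports by time point and course, and a by-visit table is compatible with its words. Read that way, each woman gives one sample per visit and course, and counting samples is close to counting women. This stands. A reader might infer that the plan pools pre-dose and post-dose sera, but that is an inference from silence. What the text supports is that pooling is permitted.

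The same holds for for-cause samples. Protocol 14.7.1 says they may be analyzed; neither document says they enter the percentage. They are simply not kept out.

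A reader might also treat Day 1 results as pre-exposure negatives and conclude that the figure will be about half the true rate. The documents do not support this. Day 1 precedes only the open-label dose. Women given active drug in the parent study, and women starting a second course, have already been exposed. With 50% positive at Day 1 and 90% at Day 71, the combined figure is 70%, not half of 90%.

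Two further limits are fair. Neither objective names neutralizing antibody, binding antibody is the listed immunogenicity variable, and no test or decision rests on the neutralizing summary. The SAP also describes visits out to Day 720 that are absent from the Amendment 2 text available here, so 14.7.1 should be checked in the protocol version the SAP follows.

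None of this supplies what is missing. Even by visit, the plan has no paired comparison, no prior-exposure split, no subset rule and no separation of triggered samples.

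**Conclusion.** The concern holds in a limited form. SAP 7.7 sets a sample-based percentage without visit, course, prior exposure, a per-woman denominator or pairing. A literal implementation could therefore produce a figure that reflects the testing mix. Such a figure cannot show how many women develop neutralizing antibody or had it before re-exposure.

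The size of the distortion is unknown. The documents give no positivity rates, no subset size and no number of added samples. The worked figures show the direction and the dependence on mix, and they rest wholly on assumed rates and on Day 1 positives staying positive. This is a descriptive secondary summary, so the change is worth making but nothing primary depends on it.

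**What to change.** Rewrite the last paragraph of SAP 7.7 to say:

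- For neutralizing anti-AUX-I and anti-AUX-II separately, report the number of women positive over the number tested, with one result per woman per visit and course. Give Day 1 and Day 71 separately, and Day 360 only if it is assayed.
- Break this down by treatment course and by prior EN3835 exposure.
- Among women with both samples tested, report the proportion negative at Day 1 and positive at Day 71.
- Fix the subset before any results are seen, and test both samples of each chosen woman where available.
- List samples tested because of results or clinical signs separately, outside the percentages.
- State how a serum shared between the end of one course and the start of the next is counted.

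The cost is SAP wording, table shells and a pick list for sera already scheduled. No extra draw is needed. For a fixed number of assays, pairing means fewer different women, and cells by course and prior exposure may be small. Counts should therefore be shown beside every percentage.

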8. HANDLING OF MISSING DATA

8.1. Handling Missing Data on Efficacy Variable

Subjects may have missing data on observational visits at Day 90, Day 180, Day 270, Day 360, and some long-term durability visits, Day 450, Day 540, Day 630 and Day 720. The backward imputation method will be utilized for the values of CR-PCSS and PR-PCSS. For instance, if a subject missed Day 90, Day 180 visits, but he/she has values at Day 270. Then the values at Day 270 will be imputed for the values at Day 180, and Day 90 visits.

No imputation will be applied to other cellulite assessments

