12.1.3. Study Entry/Observational Assessments

A subject who gives written informed consent and who satisfies all eligibility criteria (section 11) may be entered into the observational phase of the study and complete safety and cellulite severity assessments at 3-month intervals as detailed in Table 2. The first visit will be determined by the date of enrollment in study EN3835-202 relative to the Schedule of Events for study EN3835-202 (Table 2). For example, if a subject enrolls after the Day 90 visit window, the first observation visit for that subject would be Day 180. In addition, once the study drug blind is broken in study EN3835-201, enrolled subjects will be asked if they wish to receive additional open-label treatments. If a subject elects to receive open-label treatment, study assessments will be conducted in accordance with Table 3. The subject identification number will be carried over from the double-blind, placebo-controlled study (EN3835-201).

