12.1.3.1. Three-Month Assessments

Subjects will return within 20 days (± 4 days) of completion of the double-blind study for the first of 4 safety and cellulite severity evaluation visits. Assessments to be completed at these visits are detailed in Table 2. Subjects are to return at 3-month intervals until they have completed 12 months from Day 1 of the double-blind study. At these visits, the quadrant previously treated with EN3835 in the EN3835-201 study or quadrants treated with EN3835 in the open-label study

will be evaluated. If the quadrant treated in study EN3835-201 is retreated in the open-label study, the 3-month assessments will reset to treatment visit 1/Day 1 of the open-label treatment and the study visits will continue as described in [Table 3](#) followed by 3-month assessments as described in [Table 2](#). If a different quadrant is treated in the open-label study, the 3-month assessments of both the quadrant treated in the double-blind study (EN3835-201) and the quadrant treated in the open-label study will continue.

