2. ANALYSIS POPULATIONS AND PHASES

The following populations will be considered in the statistical analysis of the study:

- Observation Population: The Observation population includes all subjects rolled over from study EN3835-201. The cellulite assessment evaluations and safety analyses on data collected during observation phase will be performed using this population.
- Safety Population: The Safety population will include all subjects who receive at least 1 dose of EN3835 in the current study. All safety analyses for the treatment phase will be performed using this population. For by region summaries, safety population is considered within each treatment course.
- Effectiveness Population: The Effectiveness population includes all safety subjects who have a baseline and at least 1 post-baseline assessment on both the CR-PCSS and PR-PCSS on the quadrant selected for treatment in the current study. All analysis of effectiveness for the treatment phase will be based on this population. For by region summaries, effectiveness population is considered within each treatment course.
- Durability Population: This population is defined as all active responders who have both CR-PCSS and PR-PCSS at 180 days or above. The active responders are subjects treated with EN3835 with improvements of at least 1 level on each

scale (CR-PCSS and PR-PCSS) at Day 71 visit compared to the baseline. Analysis of durability of treatment effect will be performed using this population.

- Durability Population for Double-blind Treated Subjects: This population is defined as all subjects in the durability population who showed an improvement of at least 1 level on each scale (CR-PCSS and PR-PCSS) at Day 71 visit compared to the baseline for the quadrant treated with EN3835 in double-blind study EN3835-201.
- Durability Population for Open-label Treated Subjects: This population is defined as all subjects in the durability population who showed an improvement of at least 1 level on each scale (CR-PCSS and PR-PCSS) at Day 71 visit compared to the baseline for the quadrant treated with EN3835 in the open-label study EN3835-202 study, who did not have the same quadrant treated with EN3835 in double-blind study EN3835-201. For by region summaries, this population is considered within each treatment course.

The following 2 phases will be summarized in the statistical analysis of the study:

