6.3. Durability of Treatment Effect

The durability of treatment effect will be accessed based on the longitudinal responses of cellulites assessments of CR-PCSS and PR-PCSS. The number and percentage of responders at each level (ie, 1 level or 2 levels improvements) for CR-PCSS, PR-PCSS and their combinations (ie, composite score, 1 level or 2 levels improvements for both scores) associated with treated quadrants will be summarized by study day. The treatment failure is defined as active responders whose CR-PCSS and PR-PCSS return to the baseline or worse in an EN3835-treated quadrant during a certain follow-up period. The number and percentage will be summarized by study day, ie, Day 180, Day 360, Day 540, and Day 720.

Since there are 2 groups of responders, one group was subjects who were treated with EN3835 in the double-blind EN3835-201 study and followed up in the current EN3835-202 study up to 2 years. The durability analysis described above for this group will be based on the durability population in double-blind treated subjects. The other group will be subjects who will be treated with EN3835 and then followed up to 1 year in the current EN3835-202 study. The durability analysis for this group will be based on the durability population in open-label treated subjects.

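### SAP 8.1 fills missing CR-PCSS and PR-PCSS ratings backward from later visits, which biases the by-day durability tables, is not explicitly stopped at re-treatment, and leaves dropout unaddressed

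*Combined protocol and SAP*

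**What the plan says.** SAP 8.1 covers missed visits at Days 90, 180, 270 and 360 and at the long-term durability visits (Days 450 to 720). It states "The backward imputation method will be utilized for the values of CR-PCSS and PR-PCSS". In its example a subject misses Days 90 and 180 and is rated at Day 270: "Then the values at Day 270 will be imputed for the values at Day 180, and Day 90 visits". For everything else, "No imputation will be applied to other cellulite assessments". SAP 8.1 has no rule for a subject without a later rating.

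SAP 6.3 tabulates 1-level and 2-level responders by study day on each scale and on the composite. It then defines failure: "The treatment failure is defined as active responders whose CR-PCSS and PR-PCSS return to the baseline or worse in an EN3835-treated quadrant". For failures, "The number and percentage will be summarized by study day, ie, Day 180, Day 360, Day 540, and Day 720". The population for these tables is set in SAP 2: "This population is defined as all active responders who have both CR-PCSS and PR-PCSS at 180 days or above".

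Two protocol rules leave visits blank by design. Under Protocol Amendment 2, 12.1.3, "if a subject enrolls after the Day 90 visit window, the first observation visit for that subject would be Day 180". Under 12.1.3.1, if the quadrant treated in EN3835-201 is treated again, "the 3-month assessments will reset to treatment visit 1/Day 1 of the open-label treatment".

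**The concern.** Durability asks whether the effect is still present at a given visit. Backward filling answers that for a missed visit with a state seen later, after more time for the effect to wear off. If relapse is permanent, some women who were still responding are counted as failed, and the early columns of the table are too high.

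The error can also run the other way. If a quadrant is treated again and the next rating on the same clock comes after that second course, copying it back would show a response at a visit where the first course had already failed.

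The rule also does nothing for women who leave, because they have no later rating to copy. Dropout is the form of missingness most likely to be related to outcome. At stake are the by-day durability percentages for quadrants treated in either study.

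**Working it through.** The plan states no figure to reproduce, since neither document gives a relapse or missingness rate. All rates below are assumptions.

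**1. The SAP's own example.** A woman responds at Day 71, misses Days 90 and 180, and is back at baseline at Day 270. Take her true relapse time as uniform on Days 71 to 270, a span of 199 days.
- Already relapsed at Day 90: (90 − 71)/199 = 9.5%.
- Already relapsed at Day 180: (180 − 71)/199 = 54.8%.

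The fill records failure at both visits. It is wrong at Day 90 with probability 90.5% and at Day 180 with probability 45.2%.

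**2. Effect on the Day 180 failure percentage.** Assume permanent relapse, exponential from Day 71, reaching 25% at Day 360, so F(t) = 1 − 0.75^((t − 71)/289). This gives F(180) = 10.28%, F(270) = 17.97% and F(360) = 25.00%. Each visit is missing independently with probability m. With ratings up to Day 360, the Day 180 value after filling is

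[(1 − m)F(180) + m(1 − m)F(270) + m²(1 − m)F(360)] / (1 − m³).

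The divisor is the chance of at least one rating from Day 180 on, which matches the entry rule of the Durability Population. For m = 0.3: (0.7 × 10.28 + 0.21 × 17.97 + 0.063 × 25.00)/0.973 = 12.9%.

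| Missing per visit | True Day 180 | Observed only (expected) | Filled |
|---|---|---|---|
| 10% | 10.3% | 10.3% | 11.1% |
| 20% | 10.3% | 10.3% | 12.0% |
| 30% | 10.3% | 10.3% | 12.9% |
| 50% | 10.3% | 10.3% | 14.6% |

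If ratings stop at Day 360, the Day 360 figure cannot move. If they run to Day 720, as for quadrants treated in EN3835-201, the same sum extended to eight visits gives 25.7%, 26.6% and 27.6% at Day 360 for 10%, 20% and 30% missing, against a true 25.0%.

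A separate simulation used 400,000 subjects per scenario, exponential relapse from Day 0 reaching 20% or 40% by Day 360, and 10% to 30% missing per visit. The shifts were about +0.5 to +4 points at Day 180 and +0.5 to +3 points at Day 360. Observed ratings were unbiased.

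**3. Dropout.** In the same simulation, take 20% intermittent missingness and 5% dropout per visit, rising by 20 points after relapse:

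| True Day 360 failure | Observed only | Filled |
|---|---|---|
| 20.0% | 12.4% | 12.7% |
| 39.9% | 26.8% | 27.5% |

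Filling recovers almost none of the loss. SAP 3.1 by default divides by all subjects in the column. With that denominator the filled figures fall further, to 10.8% and 21.7%.

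**4. Copying across a re-treatment.** This is a reading of the text and has no rate attached.
- SAP 1.1 lets a woman treated with active drug in EN3835-201 have the same quadrant treated again once its scores are back at or above the EN3835-201 baseline.
- Her 3-month visits then restart, so later visits on the EN3835-201 clock go blank.
- The long-term visits in SAP Table 4 are counted from Day 1 of EN3835-201 and rate the quadrant treated there.
- An improved rating at Day 450 could therefore fill Day 360.

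**The case against.** The best defence has four parts.

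*Direction and setting.* For permanent relapse the error makes EN3835 look less durable, in an uncontrolled, descriptive study whose primary objective is safety. That is true, but it holds only for permanent relapse. If ratings fluctuate, or if a fill crosses a re-treatment, a later good score can erase a relapse. The rule cannot be relied on as conservative.

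*Size.* A reader who runs the same calculation at Day 90 finds failure rising from 1.9% to 5.1% at 30% missing and 7.8% at 50%, and might report a three- to four-fold overstatement. SAP 6.3 does not tabulate failure at Day 90. Only responder percentages can appear there, and these were not simulated. Nor does SAP 6.3 estimate a relapse time, so the harm is to percentages by visit. The protocol's duration-of-response endpoint (17.5.2) is not carried into SAP 6.3.

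*Re-treatment.* A reader might infer that nothing prevents a copy across treatment. There are partial guards:
- SAP 2 ends the observation phase at the first EN3835-202 treatment of the same quadrant, and SAP 9 says results are summarised by phase.
- The open-label durability population leaves out quadrants already treated with EN3835 in EN3835-201.
- Footnote f of SAP Table 2 directs women with a different quadrant treated to the later visits, although SAP 1.1 is worded more broadly.
- A woman re-treated in her EN3835-201 quadrant has the relapse recorded at Screening B.

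These guards do not close the gap. SAP 8.1 is not tied to phase, and the treatment phase does not break at a second course in the same quadrant. The double-blind durability population has no exclusion or censoring for re-treated quadrants. Screening B is not one of the tabulated study days.

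*Late enrollees and display.* It is tempting to say that late enrollees' Day 90 ratings are always imputed. They are filled only when a later rating exists, and the number of such women is unknown. It is also tempting to say that filled values will be shown as if observed. Neither document says how they will be displayed or flagged.

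**Conclusion.** The rule is wrong as written for a durability analysis. Under random missingness and permanent relapse it adds bias where observed ratings have none. With 25% relapse by Day 360, the Day 180 failure rate rises by about 0.8 to 4.3 points (from 10.3% to between 11.1% and 14.6%) over 10% to 50% missing. Day 90 responder percentages are affected too, including those of women who enter at Day 180 and have a later rating.

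These sizes are illustrative, because the relapse rate, its permanence and the missingness are all assumed. The possible copy across a re-treatment is an unclosed gap that the SAP does not prescribe. It would act in the opposite direction, so the net direction is unknown. The failure to address dropout follows directly from the text.

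**What to change.** Delete backward filling as the primary method in SAP 8.1.
- **By-day summaries:** use observed CR-PCSS and PR-PCSS ratings, with the number assessed at that visit as denominator, and state this as an exception to SAP 3.1.
- **Durability:** treat failure as interval-censored between the last non-failed and the first failed rating, and censor at re-treatment of that quadrant. For a quadrant treated in EN3835-201 and then re-treated, the qualifying Screening B rating already meets the failure definition, so count it before censoring.
- **Filled version, if kept as a sensitivity analysis:** fill only when the ratings on both sides agree, and only within the same quadrant and treatment course.
- **Dropout:** add a sensitivity analysis, for example counting dropouts as failures. Observed-rating summaries do not correct for relapse-related dropout, and the interval-censored estimate assumes dropout is non-informative.

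The cost is a change of SAP wording, smaller n at some visits and slightly more analysis work. No new data are needed.
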